4 OBJECTIVES AND ENDPOINTS

Table 4-1: Objectives and Endpoints

Objectives	Endpoints

Primary
 
 To assess the incidence of high grade (CTCAE v4 Grade 3-4 and Grade 5) IMAEs in participants with advanced or metastatic RCC who are treated with combination therapy of nivolumab 6 mg/kg + ipilimumab 1 mg/kg every 8 weeks alternating with nivolumab 480 mg flat dose every 8 weeks, staggered every 4 weeks (Cohort 1) To assess the incidence of high grade (CTCAE v4 Grade 3-4 and Grade 5) IMAEs in participants with advanced or metastatic RCC who are treated with combination nivolumab (3 mg/kg) and ipilimumab (1 mg/kg) every 3 weeks for four doses, followed by maintenance nivolumab (480 mg every 4 weeks), in the select subgroups of mRCC participants (nccRCC, asymptomatic brains metastasis, or any histology with KPS 50-60% (Cohorts 2, 3, 4)) 	
 incidence of high grade (CTCAE v4 Grade 3-4 and Grade 5) IMAEs

Secondary
 
 To characterize the outcome of all high grade (CTCAE v4 Grade 3-4 and Grade 5) IMAEs in participants with advanced or metastatic RCC who are treated with combination therapy in different cohorts. To assess efficacy of nivolumab in combination with ipilimumab by measuring, progression-free survival (PFS 1 at time of initial progression; objective response rate (ORR), time to response (TTR), and duration of response (DOR), in all treated participants in different cohorts using RECIST 1.1. 	
 Characterization of outcome of all high grade (CTCAE v4 Grade 3-4 and Grade 5) IMAEs (eg, time to onset, time to resolution, percentage of patients who received immune modulating medication) PFS 1, ORR, TTR, DOR

Table 4-1: Objectives and Endpoints

Objectives	Endpoints

[REDACTED]
	
[REDACTED]

[REDACTED]
	
[REDACTED]

[REDACTED]
	
[REDACTED]

[REDACTED]
	
[REDACTED]

[REDACTED]
	
[REDACTED]

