10.2 Populations for Analyses

For purposes of analysis, the following populations are defined:

Population	Description
Enrolled	All enrolled participants: all participants who signed an informed consent form and were registered into the IVRS.
Treated	All treated participants: all participants who received any nivolumab. This is the primary population for safety and efficacy analyses. .
Response Evaluable	All response evaluable participants: all treated participants who have baseline and at least one on-study evaluable tumor measurement.

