10.3.1 Efficacy Analyses

Endpoint	Statistical Analysis Methods
Primary	Not applicable

Endpoint	Statistical Analysis Methods
Secondary	
PFS will be summarized by KM product-limit method for all treated participants and all response evaluable participants, respectively. Median values of PFS, along with two-sided 95% CI using Brookmeyer and Crowley method, will be calculated. Associated two-sided 95% CIs will be calculated using the Greenwood formula. This analysis will be performed for all treated participants and for all response evaluable participants for both PFS 1 as secondary endpoint and PFS 2 as exploratory endpoint.
 
The ORR will be summarized by binomial response rates and their corresponding two-sided 95% exact CIs using the Clopper-Pearson method. This analysis will be performed for all response evaluable participants.
 
Time to response (TTR) is analyzed using the KM methodology, for all evaluable participants. KM curve was to represent the cumulative rate of response over time. For the non-responders, time to response was censored at the maximum time of response + 1 day of all participants in their respective treatment group.
 
The assessed DOR will be summarized for all response evaluable participants who achieve confirmed PR or CR using the Kaplan-Meier (KM) product-limit method. Median values of DOR, along with two-sided 95% CI using Brookmeyer and Crowley method, will also be calculated. In addition, the percentage of responders still in response at different time points (3, 6, 12, 18, and 24 months and at end of study) will be presented based on the DOR KM plot. This analysis will be performed for all response evaluable participants who achieve confirmed PR or CR.

[REDACTED]	[REDACTED]

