Death without progression and without subsequent anti-cancer therapy	Date of death	Progressed

3. **ORR:** ORR is defined as the number of subjects with a best overall response (BOR) of CR or PR divided by the number of response evaluable subjects. BOR is defined as the best response designation, as determined by the investigator, recorded between the date of first dose and the date of objectively documented progression (per RECIST 1.1 or Clinical) or the date of subsequent therapy, whichever occurs first. For subjects without documented progression or subsequent therapy, all available response designations will contribute to the BOR determination. For subjects who continue treatment beyond progression, the BOR should be determined based on response designations recorded up to the time of the initial RECIST 1.1 defined PD or clinical progression, whichever occurs first.
4. **TTR:** TTR is defined as time from the date of first dose to first documented CR or PR. Cohort 1 subjects who do not have a CR or PR will be censored at the maximum time of response + 1 day. Subjects who do not have a CR or PR in combined cohort 2, 3 and 4 will be censored at the maximum time of response in combined cohort +1 day.
5. **DOR:** DOR will be computed for subjects who achieve PR or CR only. The DOR is defined as the time between the date of first confirmed response to the date of the first documented tumor progression (per RECIST 1.1), or death due to any cause, whichever occurs first. Subjects who neither progress nor die will be censored on the date of their last evaluable tumor assessment. Subjects who received any subsequent anti-cancer therapy on or after the

date of first confirmed response will be censored at the last evaluable tumor assessment prior to or on the date of initiation of the subsequent anti-cancer therapy.

[REDACTED]

[REDACTED]

[REDACTED]

[REDACTED]

[REDACTED]

[REDACTED]

[REDACTED]

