6.3 Populations for Analyses

The following analysis populations are defined for this study:

- Enrolled subjects: All subjects who signed an informed consent form and were registered into the IVRS.
- Treated subjects: All subjects who received any nivolumab. This is the primary population for safety and efficacy analyses.

- Response evaluable subjects: All treated subjects who have baseline and at least one on-study evaluable tumor measurement. Refer to the efficacy analysis section for the analyses conducted on this population.
- Intermediate/Poor Risk Subjects: All Treated subjects with baseline IMDC prognostic score ≥ 1 (IVRS).
- Favorable Risk Subjects: All Treated subjects with baseline IMDC prognostic score = 0 (IVRS)
- PD-L1 treated subjects: All subjects with a PD-L1 assessment at baseline who received any dose of study therapy.

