7.5.1.2 Objective Response Rate and Clinical Benefit Rate

The Objective Response Rate (ORR) and Clinical Benefit Rate (CBR) will be summarized by binomial response rates and their corresponding two-sided 95% exact CIs using the Clopper-Pearson method. This analysis will be performed for all response evaluable subjects for all cohorts and response evaluable intermediate/poor risk subjects and all response evaluable favorable risk subjects will be presented only for Cohort 1. The BOR will be tabulated.

Listings of BOR, per time point tumor response, and lesion evaluations will be provided.

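### ORR is divided by response evaluable subjects although the objective is set in all treated participants, so the visible ORR analysis can only overstate the response rate

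*SAP*

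**What the plan says.** The secondary efficacy objective (Protocol Section 4, repeated in SAP 3.2) covers PFS 1, ORR, TTR and DOR "in all treated participants in different cohorts using RECIST 1.1". Protocol 10.2 defines the Treated population as "all participants who received any nivolumab. This is the primary population for safety and efficacy analyses", and SAP 6.3 gives it the same role: "This is the primary population for safety and efficacy analyses".

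The ORR analysis uses a narrower set:

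- SAP 4.2 defines ORR as the number of subjects with a "best overall response (BOR) of CR or PR divided by the number of response evaluable subjects".
- SAP 7.5.1.2, which also covers the clinical benefit rate (CBR), says: "This analysis will be performed for all response evaluable subjects for all cohorts".
- Protocol 10.3.1 specifies "exact CIs using the Clopper-Pearson method. This analysis will be performed for all response evaluable participants".

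SAP 6.3 defines the response evaluable set as "All treated subjects who have baseline and at least one on-study evaluable tumor measurement". Protocol 9.1 schedules the first on-study scan at Week 12 (± 1 week).

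PFS is handled differently. Protocol 10.3.1 states: "PFS will be summarized by KM product-limit method for all treated participants and all response evaluable participants, respectively". SAP 7.5.1.1 analyses PFS 1 in all treated subjects.

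**The concern.** The subjects removed from the denominator are treated subjects who never have an evaluable on-study measurement. The likely reasons are death, clinical deterioration or withdrawal before the Week 12 scan; this is inference, as the documents do not list reasons. Such subjects are treatment failures or unknowns, and none can count as a response. Someone who dies before Week 12 without a scan, a recorded progression or subsequent therapy is an event for PFS 1 under SAP Table 4.2-1 but disappears from ORR.

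Three things are at stake.

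- The reported ORR does not answer the objective as written.
- The overstatement depends on early loss, which may differ between cohorts. SAP 7.1 itself says that tolerability in Cohort 4 may differ from the other groups because of its low KPS. By-cohort ORRs would then be overstated by different amounts.
- The time-to-response curve for all cohorts (SAP 7.5.1.3) uses the same evaluable set and carries the same overstatement.

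**Working it through.** **Plan's own figure.** The documents give no expected ORR, ORR precision or expected non-evaluable share. Their only precision figures (Protocol 10.1, SAP 5) are 95% CI half-widths for high-grade IMAE rates: 9.3% to 9.8% for 100 participants and 6.6% to 6.9% for 200. These reproduce with 1.96 × √(p(1 − p)/n): 9.28% at p = 0.34 and 9.80% at p = 0.50 for n = 100, and 6.57% and 6.93% for n = 200. They have no bearing on ORR.

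**Inputs from the documents.** Planned cohort sizes are 100, 50, 25 and 25 (SAP 5). The ORR interval is the two-sided exact 95% Clopper-Pearson interval (SAP 7.5.1.2).

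**Assumed inputs.** The non-evaluable share m is taken as 5% to 30%, and the all-treated ORR as 20% to 40%.

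**Step 1, the numerator.** A CR or PR needs a baseline and an on-study measurement, and Protocol Appendix 4 (3.3.3) also requires confirmation at least 4 weeks later. A non-evaluable subject cannot be a responder, so the number of responders R is the same in both sets.

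**Step 2, the ratio.** With N treated subjects:

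ORR(evaluable) / ORR(treated) = [R/(N − mN)] / [R/N] = 1/(1 − m)

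This exceeds 1 whenever m > 0 and R > 0.

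**Step 3, Cohort 1 at N = 100.**

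| m | Factor | R = 20 (20.0% of treated) | R = 30 (30.0%) | R = 40 (40.0%) |
|---|---|---|---|---|
| 5% | 1.05 | 20/95 = 21.1% | 30/95 = 31.6% | 40/95 = 42.1% |
| 10% | 1.11 | 20/90 = 22.2% | 30/90 = 33.3% | 40/90 = 44.4% |
| 20% | 1.25 | 20/80 = 25.0% | 30/80 = 37.5% | 40/80 = 50.0% |
| 30% | 1.43 | 20/70 = 28.6% | 30/70 = 42.9% | 40/70 = 57.1% |

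The interval moves too: 30/100 has exact limits 21.2% to 40.0%, and 30/80 has 26.9% to 49.0%.

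**Step 4, Cohorts 3 and 4 at N = 25.** Each non-evaluable subject is 1/25 = 4% of the cohort. One gives a factor of 25/24 = 1.04; five give 25/20 = 1.25. With 5 responders, 5/25 = 20.0% (exact 95% CI 6.8% to 40.7%) becomes 5/20 = 25.0% (8.7% to 49.1%). If both cohorts had 5 responders in 25 treated, with one subject not evaluable in one cohort and five in the other, the reported ORRs would be 5/24 = 20.8% and 5/20 = 25.0%, although the all-treated rates are equal.

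**Step 5, time to response.** SAP 4.2 censors non-responders one day after the longest response time. No one is censored before the last response, so the Kaplan-Meier response curve plateaus at R divided by the size of the set used. The factor in Step 2 therefore applies to the plateau as well.

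**The case against.** The strongest reply is that this is a declared, prespecified choice. SAP 7.1 makes all treated subjects the default except where the SAP states otherwise, SAP 6.3 points to the efficacy section for analyses in the evaluable set, and the protocol and SAP name the same ORR denominator. The objective's wording is also loose: it covers DOR, which can only be computed in responders. This shows that the choice was deliberate. It does not remove the upward bias, and it leaves the separate statements that Treated is the primary efficacy population.

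Second, an all-treated analysis may sit in redacted text. The SAP document history mentions additional populations for BOR and a subset section that includes ORR. This stands as a limit: the finding concerns the visible text. Even so, the unredacted definition in SAP 4.2 would still disagree with the objective.

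Third, the size is assumed, and m may be small. Imaging continues to the later of progression or treatment discontinuation (Protocol 9.1), an unscheduled evaluable scan keeps a subject in the set, and Protocol 7.9 asks for efforts to document progression after treatment stops for deterioration. Stopping treatment early therefore does not by itself exclude anyone. This stands: at m = 5% the effect is only 1 to 2 percentage points.

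Fourth, a reader could divide responders by the number treated, since BOR and disposition are tabulated. That is possible, but the headline ORR and its interval would still be the evaluable-set figures.

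**Conclusion.** The concern holds. In the visible text, ORR and CBR are planned only in response evaluable subjects, in conflict with the all-treated objective and the stated primary efficacy population. The direction is certain: the ORR can only rise, by 1/(1 − m). The size is not known, because the documents give neither m nor an expected ORR. For all-treated ORRs of 20% to 40%, the overstatement is 1 to 2 points at an assumed m of 5% and 5 to 10 points at an assumed m of 20%.

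The matter should be fixed, but it is limited to a secondary, descriptive endpoint in a safety trial. No error rate and no primary result depends on it.

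A minor side point concerns the Cohort 1 risk groups. SAP 7.5.1.2 says response evaluable for their ORR, while SAP 7.5.1.3, read literally, does not repeat that restriction for TTR. The TTR plateau and the ORR for these groups might then rest on different sets. This may be only compressed drafting.

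**What to change.** - In SAP 4.2 and 7.5.1.2, with Protocol 10.3.1 aligned, make the main ORR and CBR analysis by cohort use all treated subjects. Subjects without an evaluable on-study assessment get a BOR of NE, a category already in Protocol Appendix 4, and count as non-responders. Keep the Clopper-Pearson 95% interval.
- Keep the prespecified response evaluable ORR beside it, labelled as supportive.
- Report by cohort how many treated subjects were not evaluable, and why.
- Use the all-treated set for the cumulative response curve in SAP 7.5.1.3, and state which set applies to the Cohort 1 risk groups.

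The cost is SAP wording, one aligned sentence in Protocol 10.3.1 and one more denominator in existing tables. No further tumor assessments are needed. The headline ORR may be lower.

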4.2 Secondary Endpoints

The secondary objective of the study will be assessed by measuring the following:

1. Characterization of outcome of all high grade (Grade 3-4 and Grade 5) IMAEs: Time to onset, time to resolution and percentage of subjects who received immune modulating medication will be analyzed for high grade (Grade 3-5) IMAEs of interest. Time to onset is calculated from first dosing date to the IMAE event onset date. Time to resolution is calculated from the IMAE onset date to IMAE end date. If an IMAE is ongoing at the time of analysis, the time to resolution will be censored at the last contact date. Management of high-grade (Grade 3-5) IMAEs will be characterized according to the following for all treated subjects:
 1. Percentage of participants who received immune modulating medication (or hormonal replacement therapy),
 2. Percentage of participants who received ≥ 40 mg prednisone equivalents,
 3. Total duration of all immune modulating medications given for the event.
2. PFS 1: PFS 1 is defined as the time from first dose to the date of the first documented PD as determined by the investigator (per RECIST 1.1 criteria or clinical) or death due to any cause whichever occur first. Subjects who die without a reported PD and without subsequent anti-cancer therapy will be considered to have progressed on the date of their death. Subjects who did not progress or die will be censored on the date of their last evaluable tumor assessment. Subjects who did not have any on-study tumor assessments and did not die will be censored on the date of first dose. Subjects who received any subsequent anti-cancer therapy without a prior reported progression will be censored at the

last evaluable tumor assessment prior to or on the date of initiation of the subsequent anti-cancer therapy.

Table 4.2-1: Censoring Scheme Used in Primary Analysis of PFS 1

Situation	Date of Progression or Censoring	Outcome
No baseline tumor assessments	First dose	Censored
No on study tumor assessments and no death	First dose	Censored
Progression documented between scheduled visits (per RECIST 1.1 criteria or clinical)	Date of the first documented tumor progression	Progressed
No progression, no death	Date of last tumor assessment with no documented progression	Censored
New anticancer treatment started without a prior reported progression	Date of last tumor assessment prior to or on the date of initiation of the subsequent anti-cancer therapy	Censored

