7.5.1.4 Duration of Response

[figure not shown]
DOR will be summarized using KM product-limit method. Median values of DOR based on KM method, along with two-sided 95%CI using Brookmeyer and Crowley method, will be calculated and presented in a table.

In addition, the percentage of subjects with ongoing response at different time points (3, 6, 12, 18, and 24 months) will be presented based on the DOR KM plot.

This analysis will be performed for all response evaluable subjects for all Cohorts, all intermediate/poor risk subjects and all favorable risk subjects only for Cohort 1 who achieve confirmed PR or CR.

A by-subject listing of TTR and DOR will be provided.

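### The DOR rule in SAP 4.2 censors for subsequent therapy without excepting earlier progression; it conflicts with the DOR definition and, taken literally, overstates duration of response

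*SAP*

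**What the plan says.** SAP 4.2 item 5 defines DOR as the "time between the date of first confirmed response to the date of the first documented tumor progression (per RECIST 1.1), or death" from any cause, whichever is first. Two censoring sentences follow.

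- The first is limited to responders without an event: "Subjects who neither progress nor die will be censored on the date of their last evaluable tumor assessment".
- The second covers new therapy. It opens "Subjects who received any subsequent anti-cancer therapy on or after the" and continues "date of first confirmed response will be censored at the last evaluable tumor assessment prior to or on the date of initiation" of the new therapy. Its only condition is timing relative to the response.

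The PFS 1 rule in item 2 of the same section is conditional: "Subjects who received any subsequent anti-cancer therapy without a prior reported progression will be censored at the" last evaluable assessment before or on the start of that therapy. Table 4.2-1 repeats the condition in its row "New anticancer treatment started without a prior reported progression". No corresponding table for DOR is visible.

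SAP 7.5.1.4 says "DOR will be summarized using KM product-limit method", with a median, a 95% CI and the percentage still in response at 3, 6, 12, 18 and 24 months. Neither that section nor Protocol 10.3.1 gives a DOR censoring rule.

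**The concern.** A responder who progresses and then starts new therapy satisfies both the event definition and the therapy-censoring sentence, and the SAP does not rank them. Such records will be identifiable: Protocol Table 2-5 collects subsequent anti-cancer therapy during survival follow-up. The timing condition in the DOR sentence excludes almost nobody, because best overall response is taken only up to progression "or the date of subsequent therapy, whichever occurs first". A responder's new therapy therefore comes after the response.

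If the censoring sentence wins, only deaths and progressions with no later therapy remain as events. Progressions are then censored because the patient progressed and was treated, which is informative censoring. The same scan would be an event for PFS 1 and a censored time for DOR.

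**Working it through.** The plan states no expected DOR, so there is no figure to reproduce. The check has four steps.

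**1. Three records under each sentence** (months from first confirmed response)

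| Record | DOR definition | Therapy sentence, literal | PFS 1 rule |
|---|---|---|---|
| A: RECIST progression at 14, new therapy at 15 | Event at 14 | Censored at 14 or at a later scan up to 15 | Event at the same scan |
| B: RECIST progression at 14, no new therapy | Event at 14 | Does not apply | Event |
| C: no progression, new therapy at 15 | No event before therapy | Censored at last scan up to 15 | Censored |

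Only record A conflicts. Its censored time can fall after the progression scan. Protocol 7.9 allows treatment beyond progression with a further scan within 8 weeks, and Protocol 9.1 continues imaging to progression or treatment discontinuation, whichever is later.

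**2. Direction.** The Kaplan-Meier estimate is S(t) = product over event times u ≤ t of (1 − d/n), where d is the number of events at u and n the number at risk. Recoding a progression as censored at the same or a later time lowers d at that time and never lowers n at any time. Every factor stays the same or rises, so the literal curve cannot lie below the correctly coded one.

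**3. Example checkable by hand.** Take 10 responders: progression at 6, 8, 10, 12, 14 and 16 months, and four still in response at 24.

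- Progression as event: S(14) = 5/10 = 0.50, so the median is 14 months. S(18) = 4/10 = 0.40.
- Literal rule, with those progressing at 6, 10, 14 and 16 later treated and censored at progression: events remain at 8 (9 at risk) and 12 (7 at risk). S(18) = 8/9 × 6/7 = 0.76, and the median is not reached.
- The result depends on which four are treated. If the remaining events are at 6 and 8, S(18) = 9/10 × 8/9 = 0.80. If they are at 14 and 16, S(18) = 5/6 × 4/5 = 0.67.

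**4. Illustrative simulation.** All of these inputs are assumptions: exponential DOR; 90% of events progressions and 10% deaths; scans every 8 weeks to 13 months and then every 12 weeks, counted from response; follow-up uniform over 18–36 months; mean gap of 1.5 months from progression to new therapy; 20,000 responders per scenario; censoring at the progression scan. In each cell, the value with progression as the event comes first and the literal rule second.

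| True median (months) | Progressors starting new therapy | KM median (months) | 12-month rate | 24-month rate | Events lost |
|---|---|---|---|---|---|
| 12 | 30% | 12.9 → 17.3 | 0.53 → 0.63 | 0.27 → 0.38 | 26% |
| 12 | 50% | 12.9 → 22.8 | 0.53 → 0.71 | 0.26 → 0.48 | 44% |
| 12 | 70% | 12.9 → 31.1 | 0.53 → 0.80 | 0.27 → 0.61 | 61% |
| 18 | 30% | 20.0 → 25.5 | 0.66 → 0.74 | 0.42 → 0.53 | 26% |
| 18 | 50% | 20.0 → 33.3 | 0.65 → 0.79 | 0.41 → 0.62 | 43% |
| 18 | 70% | 20.0 → not reached | 0.65 → 0.86 | 0.41 → 0.71 | 61% |
| 24 | 30% | 25.5 → 33.8 | 0.73 → 0.79 | 0.52 → 0.62 | 26% |
| 24 | 50% | 25.5 → not reached | 0.72 → 0.84 | 0.52 → 0.69 | 44% |
| 24 | 70% | 25.5 → not reached | 0.72 → 0.89 | 0.51 → 0.77 | 60% |

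Correctly coded medians exceed the true ones because progression is detected only at scans. Placing the censoring at a later scan before therapy changed the rates by less than 1 percentage point. In 500 samples of 30 responders, the literal curve never fell below the correct one.

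**The case against.** The strongest reply is that the harmful reading is not the natural one. DOR ends at the first progression or death, so in record A the interval has closed before therapy starts, and censoring normally applies to a subject whose event has not been seen. The PFS 1 rule shows the likely intent, and a programmer could let the definition prevail and get the right answer. This stands as an argument about intent. It does not remove the conflict, because the therapy sentence is unconditional where its neighbours are conditional, and no order of precedence is given.

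Second, governing text may be unseen. Material directly after item 5 is redacted, two entries after Table 4.2-1 in the list of tables are redacted, conventions are delegated to the IO Core SAP, and table details to a Data Presentation Plan. Any of these might settle the matter. The statement that DOR has no censoring table therefore holds only for the visible text.

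Third, DOR is a descriptive secondary endpoint in non-randomised cohorts, and the primary analysis of high-grade immune-mediated events is untouched. That limits the stakes and is accepted.

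A reader might infer that the reported DOR is inflated, or that it is inflated by the amounts in the simulation. The documents support neither. They do not show which sentence was programmed, and they give no responder count, DOR, share of deaths or uptake of later therapy. Nor do they support saying that censoring always falls exactly at progression, since scans may continue after it.

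**Conclusion.** The defect holds as a conflict within SAP 4.2 item 5, caused by a condition that PFS 1 and Table 4.2-1 carry and DOR lacks. The bias is conditional: it arises only if the therapy sentence overrides the event definition. In that case its direction is certain, namely upward for the median and for every landmark rate, and DOR contradicts PFS 1 on the same RECIST progression. Its size is not identifiable from the documents. Over the assumed ranges above (true median 12–24 months, 30–70% of progressors treated), the 12-month rate rises by about 7 to 27 percentage points and the 24-month rate by about 10 to 34. These figures show only that the effect need not be small. The wording should be corrected, subject to what the redacted text and the IO Core SAP may say.

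**What to change.** In the last sentence of SAP 4.2 item 5, after the reference to the date of first confirmed response, insert: *without a prior documented progression (per RECIST 1.1)*. Leave the censoring date as it is. Then add: *A RECIST 1.1 progression documented before subsequent therapy is an event on the progression date, whether or not therapy follows.*

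Two details matter. Keep the word *confirmed*, because DOR starts at first confirmed response. Keep *per RECIST 1.1*, because PFS 1 also counts clinical progression and DOR does not; without it, clinical progression followed by therapy could be coded as a DOR event against the definition. A short DOR censoring table modelled on Table 4.2-1 would make the rule unambiguous.

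The cost is one clause, one sentence and one programming condition, with no new data. Where responders progress and then receive new therapy, the reported DOR curve will be no higher than under the literal rule, and usually lower.
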